1.0 Introduction

Heart failure (HF) is a major threat to public health affecting 5.3 million individuals in the United States (U.S.). HF is the major cause of mortality, morbidity, and hospitalization in patients aged 65 years and older. In 2008, the estimated direct and indirect cost of HF in the U.S. was 34.8 billion.¹ Several randomized clinical trials have demonstrated the benefits of heart failure patients receiving cardiac resynchronization therapy (CRT) with an implantable cardioverter defibrillator. Implantation of a CRT-D device can make it challenging to place a standard size lead in a small and tortuous vein. St Jude Medical developed a 4.7 Fr CS lead referred to as the QuickFlex®µ 1258T LV Lead. In a premarket IDE clinical trial (G080040), this new lead was successfully implanted in a high percentage of patients, had clinically acceptable bipolar electrical performance, and was associated with a few complications. The goal of this post approval study (PAS) is to characterize the chronic performance of the St Jude Medical (SJM) QuickFlex®µ 1258T lead.

2.0 Purpose

The purpose of this PAS is to evaluate the acute and chronic performance of the SJM QuickFlex®µ 1258T LV lead in a patient population indicated for implantable cardioverter defibrillator and cardiac resynchronization therapy. The QuickFlex®µ 1258T LV Lead study will be performed in compliance with the Conditions for Approval as agreed upon with the FDA.

3.0 Description of Device

In this study, the QuickFlex®µ 1258T LV Lead will be implanted with compatible legally marketed St. Jude Medical CRT-D devices.

The QuickFlex®µ 1258T left heart lead is a bipolar over-the-wire design, enabling implantation using either stylet or guidewire guided placement. The lead has an open lumen and an opening at the lead tip to allow the use of the guidewire. The lead body has Optim® (Elast-eon) insulation and a maximum lead body diameter of 4.7 Fr. Like the QuickSite® left heart lead family, the distal portion of the QuickFlex®µ 1258T left heart lead is pre-shaped in an “s-curve” configuration. The titanium nitride (TiN) coated platinum/iridium (PtIr) tip electrode contains a molded ring that elutes steroid. Additionally, the surface of the tip electrode is coated with a thin steroid film to provide immediate steroid release. A titanium nitride (TiN) coated platinum/iridium (PtIr) ring electrode is located 20 mm from the tip of the lead. The outer lead body is

¹ Heart disease and Stroke Statistics—2008 Update, American Heart Association

covered with Fast-Pass™ coating to increase lubricity during initial implant. The lead connector complies with the IS-1 connector standard ISO 5841-3.

4.0 Clinical Protocol

4.1 Study Design and Scope

The QuickFlex®µ 1258T LV Lead study is a multi-center post-approval study that will be performed in compliance with the Conditions for Approval as agreed upon with the FDA. Patients may be enrolled in the study in one of two ways. Patients who previously participated in the QuickFlex®µ 1258T LV Lead IDE study and are at a center that is participating in the post approval study may be approached for enrollment into the post approval study. In addition, newly implanted patients will be approached at participating centers for participation in the study until the enrollment criteria is met. New patients who meet inclusion/exclusion criteria will have an attempted implant of the QuickFlex®µ 1258T lead. Patients who have an unsuccessful implant will be followed for 30 days for any adverse events and then withdrawn from the study, or may have an implant reattempted if the physician chooses to do so. Patients who have a successful implant of the LV lead will be considered to have received a successful CRT-D system. Following enrollment, patients will be followed at 6 months, and every 6 months thereafter, for 60 months of follow up (5 years). After patients complete 60 months of follow-up, their participation in the study will be terminated. There will be 1,884 new patients enrolled in the study to achieve an evaluable sample size of 1036 patients. In addition, every effort will be made to enroll existing IDE patients from sites participating in the Post Approval study. [REDACTED]

[REDACTED] for a total sample size of 1,955 to 1,991 patients. [REDACTED]

[REDACTED] If implantation rate at a study site is higher than the projected estimates, then the study enrollment period will be decreased proportionately. Reporting will occur per section 4.2.3 of the protocol. In order to accomplish this, the study will be conducted at a maximum of 80 study centers.

Definitions: The following definitions will be used in the QuickFlex®µ 1258T post approval study.

Abnormal Lead Pacing Impedance: Measured pacing impedances with values $\leq 200 \Omega$ or $\geq 2000 \Omega$

Adverse Event: Any unfavorable clinical event which impacts, or has the potential to impact the health or safety of a patient caused by or associated

with a study device or intervention. Adverse events are classified as complications or observations.

Cardiac Tamponade: Confirmed or suspected accumulation of fluid in the pericardial space.

Cardiac Perforation: An excursion of the lead through the cardiac muscle. Signs and symptoms of a perforation by an intra-cardiac lead may include radiographic evidence of excursion of the lead into the pericardial sac, abnormal echocardiography indicative of a perforation, the accumulation of fluid in the pericardium, cardiac tamponade, or patient symptoms such as chest pain and discomfort.

Complication: An adverse event that requires invasive intervention to resolve (e.g., lead fracture).

Diaphragmatic/Phrenic Nerve Stimulation: Electrical activation of the diaphragm muscle by the device output pulse. The abrupt diaphragmatic contraction is noted clinically as hiccups associated with each pacing stimulus. The pacing stimulus may stimulate the diaphragm either directly or indirectly via the phrenic nerve.

Elevated Pacing Thresholds: Voltage thresholds > 3.0V at implant and 2-fold over the first chronic threshold or 3.5V at follow up.

This definition is intended to serve as a guideline and it is understood that individual patients may have unique situations.

Generator Malfunction: Suspected failure of the device to perform as indicated.

Lead Dislodgement: The movement of a pacing lead from its originally implanted position; often indicated by changes in pacing and/or sensing thresholds including loss of sensing and/or capture. Dislodgement can be confirmed by radiographic studies.

Lead Fracture: A break in a conduction coil of a pacing or defibrillation lead typically evidenced by an increase in impedance, intermittent or complete loss of capture, intermittent or complete loss of sensing, noise on the intra-cardiac electrogram and visual signs of conductor coil fracture on x-ray.

Lead Implant Attempt: An insertion of the lead into the vasculature and into the heart for positioning within a single procedure. A second attempt occurs when the lead is completely removed from the vasculature and is reinserted, or a new lead is inserted.

Lead Insulation Damage: A disruption to the integrity of the lead insulation without disruption of the conductor coil. An insulation break may be indicated by a drop in impedance, and can cause loss of capture or sensing problems.

Loss of Capture: The inability of the device's output pulse to result in depolarization and contraction of the appropriate cardiac chamber. Causes include insufficient stimulus strength, separation of the electrode from the myocardium and placement of the stimulating electrode in contact with a non-responsive portion of the myocardium such as scar tissue.

Loss of Sensing: A condition in which the pulse generator is unable to sense intrinsic cardiac signals (applicable to RA and RV lead(s)).

Observation: Adverse events that can be managed without invasive intervention (e.g., over-sensing or loss of pacing capture, which is remedied by reprogramming of the pulse generator).

Over-sensing: The detection of inappropriate electrical signals by the pulse generator’s sense amplifier. These signals, such as myopotentials, electromagnetic interference, T waves or crosstalk between atrial and ventricular channels, must be of sufficient duration to interfere with normal device function. (applicable to RA and RV lead(s))

Pneumothorax: An accumulation or suspected accumulation of air in the pleural cavity.

[figure not shown]
Successful Implant: A SJM CRT-D system with an implanted QuickFlex®µ 1258T lead.

System Implant Attempt: A procedure in which a QuickFlex®µ 1258T lead implant is attempted.

Under-sensing: The failure of the pulse generator to sense P or R waves, causing delivery of inappropriately timed, asynchronous or competitive output pulses. Under-sensing can sometimes be corrected by programming the device to a more sensitive setting, i.e., decreasing the millivolt (mV) value (applicable to RA and RV lead(s)).

Unsuccessful Implant: An attempted implant that does not result in a successful QuickFlex®µ 1258T lead implant.

4.1.1 Study Flow Diagram

4.1.2 Projected Study Timeline

A timeline for the QuickFlex®µ 1258T LV Lead post approval study is provided below. This timeline is based on initiating the study in the third quarter of 2010; dates will change based on the actual start date of the study, the date enrollment begins, and/or the actual enrollment rate.

4.2 Study Endpoints/Objectives

The endpoints of the study are:

- Complication free survival rate at 5 years for complications related to the LV lead
- Electrical performance (capture threshold) of St. Jude Medical's QuickFlex® μ 1258T LV Lead

The study will also characterize the complication rates and perform a trend analysis for all complications related to the LV lead.

4.2.1 Primary Endpoint 1 – Freedom from LV Lead-Related Complications

We will test the following hypothesis for LV lead related complication free survival at 5 years:

H_0 : Complication free survival at 5 years \leq 92.5%

H_1 : Complication free survival at 5 years $>$ 92.5%

The desired outcome is to reject the null hypothesis. The null hypothesis will be rejected at the 5% significance level if the 95% Lower Confidence Bound (LCB) for the freedom from complications is greater than 92.5%.

Sample Size

Analysis

All complications will be classified as related to the LV lead or as unrelated. The following complications will be included in the LV lead related analysis:

- Cardiac perforation
- Lead dislodgement that occurred greater than 30 days after implant
- Lead insulation damage
- Lead fracture
- Diaphragmatic/Phrenic nerve stimulation

- Abnormal LV lead performance (abnormal lead pacing impedance, elevated pacing thresholds, and loss of capture,)
- Other unexpected complications that are considered related to the LV lead

All patients who had an attempted implant of the QuickFlex μ 1258T LV Lead will be included in the analysis of this endpoint. The survival time for all patients will be calculated as the number of days from implant or attempted implant to the date the complication was first discovered. For patients who do not experience a complication related to the LV lead at the time of their withdrawal, the survival time will be censored on the date of their withdrawal. For patients who have not experienced any complication related to the LV lead at the time of analysis, the survival time will be censored on the date of analysis. This analysis will also include all IDE study patients from sites that agree to participate in the PAS study. Patients from these sites who participated in the IDE study, but who do not consent to participate in the PAS study will be included in the analysis. If event free, they will be censored at the time of approval of the QuickFlex μ 1258T LV Lead or the last IDE follow-up visit (whichever is later). This will ensure that there is no bias in the estimates of complication rates; site selection criteria are independent of complication rates. The endpoint will be evaluated using the Kaplan-Meier method and the 95% lower confidence bound (LCB) will be obtained by transformation from its log scale, based on Peto et al². The null hypothesis will be rejected if the 95% LCB is greater than 92.5%. Kaplan-Meier curves will also be presented for each adverse event category of complication listed above.

A sub-group analysis will be performed to compare the LV lead related complication rates in patients rolled over from the IDE study to newly enrolled patients. Complication free survival estimates will also be estimated for the newly enrolled and IDE subjects by stratification in the Kaplan Meier analysis. The two groups will be compared using the log-rank test. As with the primary analysis, the sub-group analysis will include all IDE study patients from sites that agree to participate in the PAS study. Patients from these sites who participated in the IDE study, but who do not consent to participate in the PAS study will be included in the analysis. If event free, they will be censored at the time of approval of the QuickFlex μ 1258T LV Lead or the last IDE follow-up visit (whichever is later). This will ensure that there is no bias in the estimates of complication rates; site selection criteria are independent of complication rates.

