10.0 Withdrawals

Withdrawal is defined as termination of participation of a patient from a clinical trial. All reasonable efforts should be made to retain the subject in the clinical trial until completion of the clinical trial. Reasons for withdrawal include, but are not limited to the following:

- Heart Transplant
- Patient Death
- Patient and/or Family Request
- Patient Lost to Follow-Up - Defined as the following: Patient will be considered "lost to follow-up" after a minimum of two documented phone calls were made by personnel at the study center to the patient or emergency contact, a certified letter was sent to the last known address, and two consecutive visits pass without an investigator receiving data
- Patient Non-compliance
- Patient Participation terminated by Investigator
- Sponsor Request
- System explanted without a system replacement
- Unsuccessful Implant
- Removal of the QuickFlex® μ 1258T lead without a QuickFlex® μ 1258T lead replacement

Complete a Withdrawal Case Report Form and record all results. If the patient experienced an adverse event or protocol deviation, complete an Adverse Event and/or Deviation Case Report Form. Send the forms to St. Jude Medical, CRMD Sunnyvale, CA.

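### Endpoint 1's Kaplan-Meier figure is lead survival net of death and other competing events; its complement overstates, and the crude proportion in 4.2.3 understates, the share of patients with an LV-lead complication by 5 years

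*Protocol*

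**What the plan says.** **The test.** Protocol section 4.2.1 announces: "We will test the following hypothesis for LV lead related complication free survival at 5 years". The decision rule is: "The null hypothesis will be rejected at the 5% significance level if the 95% Lower Confidence Bound (LCB) for the freedom from complications" exceeds 92.5%. The estimator is fixed as well: "The endpoint will be evaluated using the Kaplan-Meier method and the 95% lower confidence bound (LCB) will be obtained by transformation from its log scale".

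**Censoring.** The rule for patients who leave event-free reads: "For patients who do not experience a complication related to the LV lead at the time of their withdrawal, the survival time will be censored". The date used is that of withdrawal. Section 10.0 opens its list with "Reasons for withdrawal include, but are not limited to the following". The list holds loss to follow-up and patient request, and also death, heart transplant, system explant without replacement, and removal of the study lead without another study lead.

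**Categories.** Section 4.2.1 adds: "Kaplan-Meier curves will also be presented for each adverse event category of complication listed above".

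**The secondary objective.** Section 4.2.3 aims to characterize the LV-lead complication rate. Its patient group is everyone with an implant or attempted implant. The final report gives the number and proportion of patients with each type of complication at 5 years, with Clopper-Pearson intervals. Section 4.2.4 adds a separate KM analysis of all-cause death.

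**Attrition.** Section 4.1 states: "There will be 1,884 new patients enrolled in the study to achieve an evaluable sample size of 1036 patients". The text explaining the attrition is redacted.

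**The concern.** A patient who has died, received a transplant or lost the lead for another reason cannot have a later LV-lead complication. That is a competing event, not an unknown outcome. KM with censoring lets such patients go on failing at the rate of those still at risk. It therefore describes lead survival if nobody died or lost the lead for other reasons, and its complement exceeds the share of patients who actually have a complication.

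The crude proportion errs the other way. Patients lost early stay in the denominator, and their later complications are never seen.

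The final report would then carry two 5-year figures, one above and one below the patient-level rate, with nothing to tell the reader so. What is at stake is the description of lead performance in this post-approval study, not the pass or fail decision.

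**Working it through.** **1. The plan's own attrition.** 1 - 1036/1884 = 0.450, and 1036/0.55 = 1,883.6, which rounds up to 1,884. As a hazard this is a = ln(1884/1036)/5 = 0.1196 per year. The 45% is back-solved, so this shows consistency only. The make-up of the 45% is not visible.

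**2. Which withdrawals compete.** Section 4.1 defines a complication as an adverse event needing invasive intervention. A removal forced by an LV-lead complication is therefore an Endpoint 1 event. What is censored is death, transplant, and removals for other reasons. Examples are infection or dislodgement within 30 days, both of which section 4.2.4 classes as unrelated to the LV lead.

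**3. Inputs and formulas.** N = 1,884; total 5-year attrition held at 45%; independent hazards. The 5-year competing share c is an assumption, because the protocol gives no figure.
- Complication hazard at the null boundary: h = -ln(0.925)/5 = 0.01559 per year
- Competing hazard: m = -ln(1 - c)/5
- Cumulative incidence: CIF = h/(h + m) × [1 - 0.925(1 - c)]
- Crude proportion seen: h/(h + a) × [1 - 0.925 × 0.55]
- SE of KM (Greenwood): 0.925 × √{ h/(h + a) × [1/(0.925 × 0.55) - 1] / N }

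**4. Worked case, c = 20%.** m = 0.04463. CIF = 0.01559/0.06022 × (1 - 0.740) = 6.73%. The gap is 7.50 - 6.73 = 0.77 points. SE = 0.925 × √(0.1154 × 0.9656/1884) = 0.71 points, so the gap is 1.08 SE. The crude proportion is 0.1154 × 0.4913 = 5.67%.

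**5. Results at 1-KM = 7.50%, constant hazard.**

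| Assumed competing share | CIF | 1-KM minus CIF | In SE | Crude | CIF minus crude |
|---|---|---|---|---|---|
| 10% | 7.12% | 0.38 | 0.53 | 5.67% | 1.45 |
| 20% | 6.73% | 0.77 | 1.08 | 5.67% | 1.06 |
| 30% | 6.32% | 1.18 | 1.65 | 5.67% | 0.65 |
| 45% (all attrition) | 5.67% | 1.83 | 2.58 | 5.67% | 0.00 |

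Differences are in percentage points. The crude figure does not vary with the share because all attrition, of either kind, ends observation. It equals the CIF only if every loss is a competing event.

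**6. Sensitivity.** At KM = 95%, shares of 10, 20 and 30% give 0.43, 0.87 and 1.34 SE. With front-loaded complications at KM = 92.5%, the same shares give 0.37, 0.76 and 1.16 SE (Weibull shape 0.5), or 0.23, 0.47 and 0.73 SE (shape 0.25). Over every case run (share 5-45%, KM 92.5-97%, constant to strongly front-loaded) the range is about 0.07 to 2.6 SE. A 2,000-run simulation at KM = 92.5% with constant hazard gave 0.52, 1.11, 1.66 and 2.60 SE for the four shares in the table.

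**7. Effect on the test.** Suppose the goal were read as a patient-level rate and the true CIF were exactly 7.5%. KM would then be about 92.1% (share 10%) or 91.6% (share 20%). Reading the bound as one-sided 5%, the chance of rejecting the null would be about 1.4% or 0.3% instead of 5%. The gap works against success.

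**The case against.** The strongest reply is that the study asks how the lead performs, and lead survival net of death is a recognised target for that. Cumulative incidence would make a lead look better the more patients die. This stands, and it is why the KM test should be kept.

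The second reply is that KM is not the only figure reported: section 4.2.3 gives observed proportions and complications per patient-year, and section 4.2.4 gives mortality. This stands as a description but does not close the gap. The crude proportion falls below the patient-level risk unless all attrition is competing, a rate per patient-year is not a 5-year risk, and a separate mortality curve does not combine the two.

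The third reply is that a supportive estimator may be left to the SAP. Its absence alone is indeed no error. But the protocol itself fixes the estimator, the censoring rule and the crude proportion, and the point concerns what those estimate.

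A reader might go further in four ways that the document does not support:
- *Section 4.2.1 claims KM is an unbiased complication rate.* Its remark on absence of bias explains why IDE patients who do not consent are included. It says nothing about competing events, and the tested quantity is named as freedom from complications.
- *All lead removals are censored.* Those required by an LV-lead complication are events.
- *The 45% is mortality.* Section 11.0 describes advanced heart failure, but section 4.4.2 excludes life expectancy under 5 years, and the composition of the attrition is not shown.
- *The category curves certainly censor a lead lost to another category.* No separate rule is given for those curves. That they follow the general withdrawal rule is an inference.

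**Conclusion.** The point holds as one of interpretation and reporting. Endpoint 1 estimates lead survival net of death, transplant and removals not counted as LV-lead complications, and the protocol does not say so. A reader might infer that the 92.5% test is invalid. It is not: under independent censoring it is correct for net lead survival, and it is conservative if read at patient level, so this feature cannot produce a false success.

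What is missing is an estimate of the patient-level 5-year complication rate. 1-KM lies above it, overall and in the category curves if they follow the same rule. The crude proportion over all attempted patients lies below it whenever part of the 45% attrition is ordinary loss. With an assumed competing share of 10-30% and constant hazards, 1-KM at 7.5% is about 0.4-1.2 points too high (0.5-1.7 SE). The gap is smaller with early complications, and the full tested range is about 0.07-2.6 SE. These sizes rest on an assumed share and hazard shape. Only the direction follows from the document.

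**What to change.** 1. In section 4.2.1, keep the KM estimate, its lower bound and the 92.5% test, and state that they refer to LV-lead survival net of death and other competing events.
2. In section 4.2.3, add the Aalen-Johansen cumulative incidence at 5 years with a 95% CI. Treat death, heart transplant, and system or lead removals not counted in Endpoint 1 as competing events. Report it as the 5-year complication rate, overall and by gender.
3. Show cumulative incidence curves for the complication categories.

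The cost is analysis wording. Withdrawal, death and product-out-of-service forms are already required, so no new data are needed. The downside is one more estimate beside the KM figure, which the sentence in step 1 should make easy to tell apart.

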4.3 Site Selection

Centers will be selected for participation in the study based on their ability to screen and enroll eligible patients, and perform the required study procedures outlined in sections 4.5 and 4.5.1. SJM will attempt to have a diversified group of centers participating in the study in the United States, including academic and non-academic institutions, [REDACTED]. To ensure a widespread distribution of data and minimize site bias, a maximum of approximately 15% of the total enrollment will be allowed at a single site.

The sites who have participated in the QuickFlex® μ 1258T Investigational Device Exemption (IDE) study will be invited to participate in this post market study. Sites who agree to participate will be instructed to approach all patients who were previously enrolled in the QuickFlex® μ 1258T Investigational Device Exemption (IDE) study for participation in the post market study for further data collection.

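### Primary Endpoint 1 takes IDE patients only from IDE sites that choose to join; neutral sponsor criteria do not make this free of bias, as the protocol claims

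*Protocol*

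**What the plan says.** Section 4.2.1 sets the IDE contribution to Primary Endpoint 1: "This analysis will also include all IDE study patients from sites that agree to participate in the PAS study". The next paragraph, on the log-rank comparison of IDE with newly enrolled patients, repeats the limit: "the sub-group analysis will include all IDE study patients from sites that agree to participate in the PAS study".

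Within joining sites the protocol guards against selection by patient. IDE patients there "who do not consent to participate in the PAS study will be included in the analysis". If event-free, they are censored at the later of lead approval and the last IDE visit. Both paragraphs then conclude: "This will ensure that there is no bias in the estimates of complication rates; site selection criteria are independent of complication rates".

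Section 4.3 describes how sites enter. The sponsor's criterion is capability: "Centers will be selected for participation in the study based on their ability to screen and enroll eligible patients". For the earlier trial, the sites of the "Investigational Device Exemption (IDE) study will be invited to participate in this post market study", and the next step concerns only those that accept: "Sites who agree to participate will be instructed to approach all patients who were previously enrolled".

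**The concern.** Two filters decide whether an IDE patient's data reach the analysis. One is the sponsor's site criteria, which do not refer to complications. The other is the site's own answer to the invitation. The no-bias statement rests on the first and does not address the second. A site answers after it has implanted the lead and seen the results, so its answer may be related to its complication count.

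The protocol already recognises this kind of selection one level down, since it keeps non-consenting patients so that consent cannot distort the rate. At site level the same route stays open. Lack of further follow-up does not explain the difference, because non-consenters have none either and are still analysed with censoring.

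At stake are the pooled five-year complication-free survival tested against 92.5% and, more directly, the IDE stratum and its log-rank comparison.

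**Working it through.** No figure in the plan is disputed, so there is none to reproduce. The check sizes the possible effect.

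**1. Share of IDE patients.** Section 4.1 gives 1,884 new patients and a total of 1,955 to 1,991; the text between is redacted.
- 1,955 − 1,884 = 71, and 71/1,955 = 3.6%.
- 1,991 − 1,884 = 107, and 107/1,991 = 5.4%.

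These may count enrolled roll-over patients only. Non-consenters would then add to the share.

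**2. Illustrative selection.** The protocol gives neither the number of IDE sites nor an IDE complication rate. Assumed: 8 patients per site, a 4% rate, and a joining probability a for sites with at least one complication and b for the others.
- P(no complication at a site) = 0.96^8 = 0.721; P(at least one) = 0.279.
- Every complication lies at a site of the first kind, so the expected rate among joining sites is a × 0.04 / (a × 0.279 + b × 0.721).
- a = 0.4, b = 0.7: 0.016 / 0.616 = 2.6%, a shift of 1.4 points.
- a = 0.2, b = 0.7: 0.008 / 0.561 = 1.4%, a shift of 2.6 points.
- Reversed, a = 0.7, b = 0.4: 0.028 / 0.484 = 5.8%, a shift of 1.8 points the other way.

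The last line is there because the protocol does not settle the direction.

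**3. Effect on the pooled estimate.** Approximate shift = IDE share × shift in the IDE rate.
- Smallest, first two cases: 0.036 × 1.4 = 0.05 points.
- Largest, first two cases: 0.054 × 2.6 = 0.14 points.
- Reversed case: 0.036 × 1.8 to 0.054 × 1.8, about 0.07 to 0.10 points in the opposite direction.

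**4. When such a shift decides the test.** Take the 95% lower bound as one-sided and set on the log scale, LCB = S × exp(−1.645 × √((1 − S)/(S × n))). Assume an effective n of 1,036, the evaluable number in section 4.1.
- S = 93.7%: LCB = 92.47%, not rejected.
- S = 93.8%: LCB = 92.58%, rejected.
- S = 94.0%: LCB = 92.79%, rejected.

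The estimate must reach about 93.7%. A shift of about 0.1 point changes the result only if the estimate lies within about that distance of this value.

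**The case against.** The case against a strong version is good, and much of it stands.

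- **The mechanism is possible, not shown.** Nothing in the protocol says that sites with poor results will decline. The joining probabilities above are assumptions, and strong ones: one complication in eight patients cuts willingness to join by 43% (0.7 to 0.4) or 71% (0.7 to 0.2). A reader might infer that the restriction favours the lead. The documents do not support that.
- **The sponsor's hold on the records is an inference.** It follows from the premarket IDE trial of this lead (section 1.0) and from the planned use of non-consenters' data, but no sentence says that data from declining sites are available.
- **A reason may exist.** Parts of sections 4.1 and 4.3 are redacted, and limiting a five-year follow-up study to participating centers is a coherent scope. It cannot be said that the exclusion lacks a reason.
- **A reader might infer that the primary result could easily flip.** Starting from 94.0% survival, a flip would need, for example, 50 omitted patients with a 20% rate (10 complications) or 107 with 15% (about 16). The illustration's own inputs, 15 to 25 sites × 8 patients × 4%, give only about 5 to 8 complications in the whole IDE trial. Those cases are not evidence of materiality.
- **The strata are shown separately.** New patients are 94.6% to 96.4% of the total (1,884/1,991 to 1,884/1,955), and the filter does not touch them. Their own estimate shows whether the conclusion leans on IDE patients. The log-rank comparison carries no stated decision rule.

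None of this rescues the statement itself. Separate strata reveal dependence on IDE patients but do not repair the IDE stratum. A coherent scope explains a restriction without making it unbiased.

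**Conclusion.** The point holds as a claim that the design does not support. The sponsor's criteria may be unrelated to complications, yet the IDE data set also depends on each site's choice, so bias is not excluded. Its direction and size are unknown.

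The effect on the primary test is probably small and decisive only close to the boundary. The IDE stratum and its comparison with new patients are more exposed. These sizes rest on the assumed site size, complication rate and joining probabilities, on an IDE share obtained by subtraction across redacted text, and on treating the pooled estimate as a simple weighted average. The correction is worth making because it is cheap; the point does not show that the primary conclusion would be wrong.

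**What to change.** In both paragraphs of section 4.2.1, replace the restriction to joining sites with IDE patients from all IDE sites. Censor event-free patients at non-joining sites at their last IDE follow-up visit. The later-of rule used for non-consenters should not be carried over, because section 6.0 arranges reporting after that visit only at participating sites, and unobserved time would count as event-free.

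If the primary population is to stay as it is, prespecify the all-sites set as a sensitivity analysis for both the primary test and the log-rank comparison.

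In either case, replace the no-bias sentence with one that claims only this: including non-consenting patients avoids selection by patient consent within joining sites.

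The sponsor should first confirm that it holds the IDE records of declining sites and may use them. If so, no new data collection is needed. The cost is slightly more programming and a second censoring rule, and the added patients contribute mainly early follow-up.
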